Group assignments will be determined by a random assignment table created by the UVM Medical Biostatistics department using PROC PLAN in SAS. The program will stratify (arrange) groups so that they are statistically similar in distribution of both gender and weight classification (BMI<30 and BMI≥30). This program will allow study personnel to access a series of envelopes that will tell them which group the participant is assigned to. A participant ID number will be permanently associated with the participant to identify which group they have been assigned to. To avoid differential impact of and to assure equal representation in each group, eligible subjects will be stratified by BMI and gender. To minimize loss to follow up, standardized training of staff will be provided focusing on rapport building, motivational interviewing and problem solving. Participants will be educated on the importance of follow up and detailed contact information is obtained at study initiation.

The Behavioral Weight Loss Program: We have developed and implemented a theory-based group-delivered behavioral weight control program in two previous studies that incorporates the elements of current thinking and empirical data on successful weight loss programs,³⁷⁻³⁹ including restricted calorie intake and increased physical activity. Key behavioral strategies to facilitate making sustained changes in dietary habits and activity patterns are introduced, promoted and reinforced throughout the program. In-person sessions facilitated by an interventionist provide the group meetings. The program provides 24 weekly facilitated group sessions over 6 months. Target weight losses of 10% of baseline weight are promoted. Behavioral strategies are drawn from social cognitive theory⁴⁰ and self-regulation theory⁴¹ and mirror the core components incorporated into such successful programs as Look AHEAD.⁴² In addition to attending weekly classes, participants will track their food intake, exercise, and weight. They will share their online tracking diaries with the group facilitator who will offer individualized feedback on their progress.

The Cooking Program

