Foods included in the ASA24 all code to the USDA's Food and Nutrient Database for Dietary Studies, and so all entries can be automatically coded.⁴³ **Healthy Eating Index (HEI)** – The HEI is a measure of overall diet quality, and can assess compliance with the U.S. Dietary Guidelines, as well as measure changes in dietary patterns. The HEI is updated with each set of Dietary Guidelines, and has been validated for the 2005 and 2010 Dietary Guidelines.⁴⁴ The HEI is a valid and reliable tool for assessing dietary quality in a variety of population subgroups and nutrition interventions.⁴⁴ The validation for the 2015 Dietary Guidelines is expected soon. The HEI takes into account one's intake of the following foods when calculating a total score, total fruit, whole fruit, total vegetables, dark green vegetables, legumes, whole grains, dairy, total protein foods, seafood, eggs, soy

products, nuts and seeds, refined grains, saturated fatty acids, polyunsaturated fatty acids, monounsaturated fatty acids, sodium, calories from added sugars, and total calories.⁴⁴ The HEI calculates final scores from 24-hour recalls like the ASA24.

Cooking and Food Provisioning Action Scale (CAFPAS): The CAFPAS scale measures cooking and food preparation practices or the degree to which individuals can set and achieve cooking and food provisioning goals. The CAFPAS includes 28 items with three subscales: Food Self-Efficacy, Food Attitude, and Structure. The CAFPAS scale has been shown to predict reported meals cooked per week and has adequate internal validity and test-retest reliability.⁴⁵

The Cooking Perceptions and Behaviors Questionnaire: The Cooking Perceptions and Behaviors questionnaire is a 53-item survey designed to assess three factors: Perceptions of Cooking, Cooking Confidence and Attitudes, and Cooking Behaviors. This survey has been used in previous research to measure cooking perceptions and behavior.⁴⁶

Weekly Assessment of Cooking Frequency: Each week, participants will use the study website to record how many times that week they cooked at home. The weekly surveys should take 5 minutes to fill out.

Height, Weight, and BMI: Measurements will be taken at the time of weekly classes. Height will be measured with a standardized stadiometer. Weight will be measured on a calibrated research scale (Tanita), and BMI will be calculated using height (m) and weight (kg) measurements.

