All participants (in both treatment conditions) will be offered small incentives such as tote bags, cookbooks, exercise equipment, gift cards, etc. (valued at approximately \$ 5-25) after completion of the follow-up data collection visits as a token of appreciation for their participation.

For research involving survey, questionnaires, etc.: *Describe the setting and the mode of administering the instrument and the provisions for maintaining privacy and confidentiality. Include the duration, intervals of administration, and overall length of participation. (describe and attach all instruments)*

Not applicable

Surveys and questionnaires will be administered online through the study website (REDCap). Participants will be sent links to questionnaires through their email. Participants will be able to save and return to questionnaires with a unique 8 digit ID provided by REDCap, however participants will not have access to review the questionnaires after completion or to make changes after submitting the forms. They will be provided with a helpline contact should they encounter difficulty in completing the forms. If participants prefer, they can complete the forms using a paper copy rather than online. It is expected that the online baseline and follow-up assessment questionnaires will take less than 30 minutes to complete and the in-person follow up assessment (weighing in) will take less than 30 minutes. The baseline and follow-up ASA24 3 day tracking is estimated to take less than 30 minutes for each entry.

Statistical Considerations: *Delineate the precise outcomes to be measured and analyzed. Describe how these results will be measured and statistically analyzed. Delineate methods used to estimate the required number of subjects. Describe power calculations if the study involves comparisons. Perform this analysis on each of the primary and secondary objectives, if possible.*

Aim 1: To determine if the addition of cooking classes to a behavioral weight control intervention improves weight loss and diet quality in overweight and obese adults.

Hypothesis 1: Weight loss and diet quality (as measured by the Healthy Eating Index) will be significantly greater in the Cooking vs. Demonstration condition at 12 and 24 weeks.

Aim 2: To evaluate changes in food agency, cooking perceptions and cooking frequency for individuals participating in the COOKING versus DEMONSTRATION conditions.

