Hypothesis 2: Food agency, cooking perceptions and cooking frequency will be significantly greater in the COOKING versus DEMONSTRATION conditions at 12 and 24 weeks.

Analysis Aims 1 and 2: The first and second hypotheses will be addressed using a repeated measures analysis of variance with treatment condition as the between group factors and assessment time as the within subject factor recalling that the baseline value will be subtracted from all subsequent values. An intent-to-treat approach will be used as the definitive analysis perspective for both the primary hypothesis testing and the secondary analysis of data. The use of a multiple imputation process will be conducted if the missing data can be assumed to be missing at random or completely at random. The intent-to-treat approach will require the use of a mixed model approach that can deal with repeated measures data and which can also deal with missing data (e.g. SAS ProcMixed or BMDP5V)

Aim 3: To explore the feasibility and acceptability of adding cooking classes to a standard behavioral weight loss intervention.

Analysis Aim 3: Feasibility and acceptability will be monitored by evaluating attendance and self-monitoring as well as qualitative data related to the perceived usefulness of the cooking classes or demonstrations.

Risks/Benefits: *Describe any potential or known risks. This includes physical, psychological, social, legal or other risks.*

Estimate the probability that given risk may occur, its severity and potential reversibility. If the study involves a placebo or washout period, the risks related to these must be addressed in both the protocol and consent. Describe the planned procedures for protecting against or minimizing potential risks and assess their likely effectiveness. Where appropriate, discuss plans for ensuring necessary medical or professional intervention in the event of adverse effects to the subjects. Discuss the potential benefits of the research to the subjects and others. Discuss why the risks to the subjects are reasonable in relation to the anticipated benefits to subjects and others. Discuss the importance of the knowledge gained or to be gained as a result of the proposed research and why the risks are reasonable in relation to the knowledge that reasonably may result. If there are no benefits state so.

Potential Risks.

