Vulnerable Populations: Explain the rationale for involvement of special classes of subjects, if any. Discuss what procedures or practices will be used in the protocol to minimize their susceptibility to undue influences and unnecessary risk (physical, psychological, etc.).

Not applicable

Number of Subjects: What is the anticipated number of subjects to be enrolled at UVM/UVM Medical Center and in the case of a multi-center study, with UVM/UVM Medical Center as the lead, the total number of subjects for the entire study.

This is a pilot study with no previous data available to calculate expected statistical power. The sample size chosen was practical as our foods lab can only accommodate 16 people at a time. Two waves of each intervention arm would give us data on approximately 64 subjects. This preliminary data will be used to determine the sample size power needed for a larger study with sufficient statistical power.

Inclusion/Exclusion Criteria: Eligibility and ineligibility criteria should be specific. Describe how eligibility will be determined and by whom. Changes to the eligibility criteria at a later phase of the research have the potential to invalidate the research.

To be eligible to participate, participants must be at least 18 years old and have a Body Mass Index (BMI) between 25-50 kg/m². Review of previous research studies conducted by this research groups has found that individuals with a BMI greater than 50 do not have success with the planned intervention. These individuals require a more intensive approach to see a

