Following informed consent, the remainder of screening will be conducted (e.g., self monitoring diary completed, discussion of randomization acceptance) and baseline data will be collected. Only those individuals with complete baseline data will be randomized.

The contact information and screening information of participants who decline consent will be destroyed.

Information Withheld From Subjects: Will any information about the research purpose and design be withheld from potential or participating subjects? If so, explain and justify the non-disclosure and describe plans for post-study debriefing.

Not applicable

Attach full grant application, including budget information and/or any contract or draft contract associated with this application.

All materials must be submitted electronically to the IRB via InfoEd. Proper security access is needed to make electronic submissions. Visit the [InfoEd Resource Materials](#) page for more information.

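### Aims 1 and 2 are analysed as raw change without the baseline value or the stratification factors, which can cost precision, chiefly for HEI and perhaps the questionnaires, but causes no bias

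*Combined protocol and SAP*

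**What the plan says.** Under Analysis Aims 1 and 2, the combined protocol and SAP plans a repeated measures analysis of variance. Condition is the between-group factor and assessment time the within-subject factor, "recalling that the baseline value will be subtracted from all subsequent values". The later sentence on a mixed model adds no covariate, and neither does any other section.

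The information needed for adjustment will be there. Study Design says that "eligible subjects will be stratified by BMI and gender", with BMI split at 30. Consent Procedures says "Only those individuals with complete baseline data will be randomized". The block size is not given; the text says only that "Group assignments will be determined by a random assignment table created by the UVM Medical Biostatistics department using PROC PLAN in SAS".

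The outcomes differ in kind. Inclusion/Exclusion Criteria names body weight as primary. Hypothesis 1 also claims that "diet quality (as measured by the Healthy Eating Index) will be significantly greater", and Hypothesis 2 covers food agency, cooking perceptions and cooking frequency. On diet quality, Quantitative Measures says "The HEI calculates final scores from 24-hour recalls like the ASA24", and the survey section says "The baseline and follow-up ASA24 3 day tracking is estimated to take less than 30 minutes for each entry".

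**The concern.** Subtracting the baseline fixes its coefficient at 1. That is close to the best choice when follow-up tracks baseline almost perfectly, as body weight may. It is wasteful when the correlation is moderate, as it may be for a diet score built on a few recall days. Omitting factors used to stratify the randomisation can also leave the reported standard error out of step with the true one.

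Kitchen capacity fixes the sample at about 64, so any extra precision has to come from the analysis. The Number of Subjects section adds that "This preliminary data will be used to determine the sample size power needed for a larger study with sufficient statistical power", so the residual SD reported from this pilot will carry forward into the next trial's sample size.

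**Working it through.** **The plan's own figure.** Number of Subjects rests on 16 places per class. 16 × 2 waves × 2 arms = 64, which reproduces the stated number. It is a capacity count; no power, SD, effect size or correlation is given.

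**Assumptions.** 32 per arm, independent participants, two-sided 5% level, one follow-up analysed by least squares. The simulations take 80% women, 65% with BMI of 30 or more, and either blocks of 4 or simple randomisation within strata. The adjusted model has baseline, gender and BMI class.

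**Step 1: formula.** Let s0 and s1 be the baseline and follow-up SDs.
- Variance of change: s0² + s1² − 2·r·s0·s1.
- Variance given baseline: s1²(1 − r²).
- Difference: (s0 − r·s1)², which is never negative.

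**Step 2: equal SDs.** The variance ratio, adjusted to change, is (1 − r²)/(2(1 − r)) = (1 + r)/2. The CI width ratio is its square root, plus about 1% for the degrees of freedom used.

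| r | √((1+r)/2) | n = 64, blocks of 4 | n = 64, simple within strata |
|---|---|---|---|
| 0.4 | 0.837 | 0.846 | 0.859 |
| 0.5 | 0.866 | 0.875 | 0.889 |
| 0.7 | 0.922 | 0.930 | 0.945 |
| 0.8 | 0.949 | about 0.96 (0.949 × 1.01) | not run |
| 0.95 | 0.987 | 0.998 | 1.013 |

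With 51 completers (20% loss) and blocks, the ratios at r = 0.4, 0.5 and 0.7 are 0.850, 0.880 and 0.936. At n = 64 the difference detectable with 80% power falls from 0.71 to 0.62 SD at r = 0.5, and from 0.55 to 0.51 SD at r = 0.7.

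**Step 3: unequal SDs.** With k = s1/s0, the width ratio is √[k²(1 − r²)/(1 + k² − 2kr)], again times about 1.01.
- k = 1.2, r = 0.67: √(0.794/0.832) = 0.977, so about 0.987. Gain about 1%.
- k = 1.2, r = 0.75: √(0.630/0.640) = 0.992, so about 1.002. No gain.
- k = 0.9, r = 0.67: √(0.446/0.604) = 0.860, so about 0.87. Gain about 13%, against about 8% at k = 1.

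**Step 4: what r might be for HEI.** If true diet quality did not change and the score behaved as a mean of three daily scores with single-day reliability ρ, r could not exceed 3ρ/(1 + 2ρ). For ρ = 0.1 to 0.6 that gives 0.25 to 0.82. This limits r, but does not by itself bound the gain. For example, take ρ = 0.4, true change independent of baseline, and k = 1.2. The three-day reliability is 1.2/1.8 = 0.667 and r = 0.667/1.2 = 0.56. The large-sample width ratio is √[(1.44 − 0.444)/(2.44 − 1.333)] = 0.949. That is a gain of 5%, against 9% (√0.833 = 0.913) at equal SDs with r = 0.667.

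**Step 5: body weight and cooking frequency.** For weight with equal SDs and r from 0.90 to 0.99, the adjusted CI runs from 1.4% narrower to 0.9% wider (blocked), or from unchanged to 2.3% wider (simple). For cooking frequency, entry is limited to 3 home-cooked meals a week. If the baseline SD is therefore half the follow-up SD and r is 0.4 to 0.7, the range is 1% wider to 3% narrower (blocked), or 3% wider to 1% narrower (simple).

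**Step 6: strata left out of a change-score model.**

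| Share of change variance explained by strata | 10% | 20% |
|---|---|---|
| Blocked: reported SE above true SE | 5% | 11% |
| Blocked: type I error | 3.9% | 3.1% |
| Blocked: cut in true SE from adjusting | 0.4% | 1.3% |
| Simple: type I error | 4.9% | 4.9% |
| Simple: cut in true SE from adjusting | 3.4% | 8.7% |

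**The case against.** The strongest case against is that nothing is invalid here. Change from baseline is an unbiased analysis under randomisation, the study is a declared pilot with no power target, and the named primary outcome, body weight, gains almost nothing. The size depends on correlations and SDs that the documents do not give. For the questionnaires, the only evidence is that CAFPAS test-retest reliability is called adequate, which is compatible with r = 0.8 or more and a gain of 4% or less. All of this stands, and it keeps the point to one of efficiency.

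The strata part is also small. Classes hold 16, and each wave splits 32 people between two arms. Simple allocation would give an exact 16/16 split only about 14% of the time, so blocking is likely. Under blocking, omission hardly changes the true standard error.

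A reader might infer that HEI gains at least some stated percentage because recall noise limits r. Steps 3 and 4 show that this needs equal SDs, which the documents do not establish. A reader might also infer that ignoring the strata inflates false positives. The simulations show the reverse under blocking, and no departure from the nominal level without it.

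On the other side, the near-zero result for body weight also depends on its assumptions. Take a baseline SD of 15 to 22 kg, a residual SD of 4 to 8 kg and a slope of follow-up on baseline of 0.90, so that heavier people lose clearly more. The raw-change CI is then about 2% to 14% wider (large-sample). At slopes of 0.95 to 1.0 it is 0% to 4% wider.

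**Conclusion.** The concern holds as a conditional loss of precision. The plan uses raw change with condition and time only, and leaves out a baseline value that every randomised participant will have. With equal SDs, 64 independent participants and blocked allocation, adjustment narrows the CI by about 15% at r = 0.4, 12% at 0.5, 7% at 0.7 and 4% at 0.8. The gain shrinks to nothing if the follow-up SD is sufficiently larger than the baseline SD, and grows if it is smaller. HEI probably has r well below 1; for the questionnaires r is unknown. Body weight at r near 0.95 and cooking frequency move by about 3% or less either way under the assumptions in Step 5. Omitting the strata under blocking mainly makes the test conservative.

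The documents do not support reading this as bias or as an invalid test. Clustering by class and bias from dropout were not assessed. The precision figures assume independent participants, and the model is not cleared on either count. The inconsistency about 12-week assessments is a separate issue and forms no part of this point.

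**What to change.** In the planned mixed model, include condition, time and condition by time, so that the 12- and 24-week hypotheses each have an estimate. Add as fixed effects the baseline value of the outcome (with baseline by time), gender and BMI class (below 30, 30 or above). Name these terms before outcome data are seen. For any measure with a single follow-up, use a week-24 ANCOVA with the same covariates. Keep raw change as a sensitivity analysis. For planning the larger study, report the adjusted residual SD and the baseline-to-follow-up correlation for each outcome.

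The cost is a few sentences and 3 to 4 of 62 degrees of freedom. Where the covariates explain nothing, the CI is about 1% wider, or 2% to 3% wider if allocation within strata is unblocked; stating the block size would show which applies. No new data are needed and no randomised participant is lost.

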Active Intervention. Twelve cooking classes will be run every other week after the in-person weight loss meetings. These lessons will be patterned after [name] cooking pedagogy and will be tailored for individuals specifically interested in weight loss. Classes will begin with a brief lecture on the day's topic, followed by a laboratory session. Participants work in teams of two in the NFS foods lab to actively practice skills and cook a meal. Subjects will receive recipes and information sheets that cover pantry supplies, grocery lists, knife skills and cooking equipment. Classes will be taught by a chef trained in the pedagogy by [name] and participants will have the opportunity to sample the food they prepared at the end of class.

Demonstrations. The demonstration condition will serve as an "attention only" control. Previous research suggests that demonstrations of cooking have little to no impact on cooking behavior, therefore, cooking demonstrations can be used to "even out" the time and attention devoted to the active cooking participants without introducing bias into the study design. Subjects in the demonstration condition will also begin with a brief lecture on the day's lesson followed by a cooking demonstration that covers the same topics as the active intervention group. All participants will receive the same printed information and also have an opportunity to sample the prepared food at the end of class. The demonstrations will be led by the same chef as the active intervention group.

Procedures: Describe all procedures (sequentially) to which human participants will be subjected. Identify all procedures that are considered experimental and/or procedures performed exclusively for research purposes. Describe the types, frequency and duration of tests, study visits, interviews, questionnaires, etc. Include required screening procedures performed before enrollment and while on study. Please provide in table, list or outline format for ease of review. (describe and attach all instruments)

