Questionnaires will be administered through the study website at baseline and study end. Participants will receive links to the questionnaires and reminders to complete questionnaires via email. These measures are outlined in greater detail below. In addition to baseline and study end questionnaires, weekly data collection will be administered through the study website. Participants will receive reminders to complete weekly data submissions, and will be given information regarding a helpline for using the study website and data entry.

Table 1 outlines when each measure will occur during the study.

Measures	Baseline	Weekly	Week 12	Week 24
ASA24				
HEI (calculated)				
CAFPAS				
Cooking Perceptions and Behaviors				
Height, Weight, BMI				
Cooking Frequency				
Photo Elicitation				
Class Evaluation				

Quantitative Measures

Automated Self-Administered 24-Hour Dietary Assessment Tool (ASA24) – The ASA24 is a web-based dietary assessment tool developed by the National Cancer Institute that allows collection of multiple, automatically coded, self-administered 24-hour recalls. The ASA24 has been validated and used in many different populations and nutrition studies.⁴³ When completing the ASA24, the participant is first prompted to report the time of all food and drinks consumed. Next, they search a list of foods and select which foods they ate at each meal. If there is a gap of more than three hours between reported eating occasions participants are then asked if they ate anything during that gap. There is then a detail pass where participants are asked about preparation methods, portion sizes and anything they added to a food. Finally, participants are asked about foods that people commonly forget to include and can add any of these foods to their recall. Detailed instructions with pictures for completing the recall are available on the ASA24 website and participants will be made aware of this resource.

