No social, legal or other risks are anticipated as part of this project. All assessment procedures and intervention recommendations have been used in previous studies without adverse outcomes. Assessment methods reflect procedures that individuals might encounter in a routine health care visit (i.e., weight assessment) or questionnaire measures that have been implemented in numerous studies without difficulties (e.g., dietary intake and physical activity questionnaires).

Intervention methods are similarly very low risk. Behavioral weight control interventions recommend that individuals make changes to dietary intake and physical activity, all of which are comparable to the recommendations made by national advisory panels and recognized leaders in health recommendations. Specifically, the intervention goals outlined are consistent with NHLBI recommendations, the American Heart Association, the American Diabetes Association, etc. These intervention

recommendations for diet and activity habit change have minimal risk. The most common risk associated with participation in the interventions is soreness or musculoskeletal injury, although this occurs infrequently. Precautions will be taken to further minimize risk by making recommendations for graded increases that slowly increase activity duration and frequency and appropriate stretching. Moderate exercise prescriptions rather than vigorous levels of physical activity should also minimize these risks.

A potential risk in the present study is that participants may fail to lose weight in the program, but this risk occurs in all approaches to weight control. Alternative approaches to weight loss, including stricter diets, pharmacological interventions, and surgical procedures, are considered to have greater risk than the dietary and physical activity program described in this protocol. Participants may utilize unhealthy dietary practices to lose weight and/or may experience minor musculoskeletal injuries during exercise; however, this is considered unlikely and precautions will be taken to further minimize this risk.

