Protection Against Risk. Every effort will be made to keep participants' information private and confidential. Confidentiality will be ensured by coding data with a unique ID number, and all data collected will be stored in locked files with access restricted to study personnel, and password protected computer data files. Participants will not be personally identified in any scientific reports generated by the study or any other dissemination efforts. All results will be presented in aggregate form. All project staff will undergo training and ongoing continuing education about methods to protect confidentiality.

Participants will be taught warm-up and stretching techniques to precede all exercise sessions to minimize the chance of muscle injury. In addition, weekly self-monitoring diaries will be submitted and reviewed at regular intervals throughout the study allowing for assessment of nutritional adequacy. No calorie goals will be set below 1200 kcal/day to provide participants with sufficient calories for a nutritionally adequate diet. Participants who become pregnant during the course of the 18-month study will be dropped from the treatment protocol, and participants who experience other medical problems during the course of the study will be referred to their personal physician for care as appropriate.

Potential Benefits

The potential benefit to the participants will be the skills and knowledge in lifestyle behaviors to successfully lose weight and prevent/deter weight re-gain. Further, participants may benefit from the improved health and psychological well-being that commonly accompanies weight loss. These benefits to the individual participant are considered substantial.

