Weekly meetings or conference calls will be held to evaluate the status of study participants. Any serious adverse events will be recorded on a standard form and reported to the Research Coordinator, to the PI's and the UVM IRB.

Withdrawal Procedures: *Define the precise criteria for withdrawing subjects from the study. Include a description of study requirements for when a subject withdraws him or herself from the study (if applicable).*

Participants may withdraw from the study at any time by notifying the PI or Study Coordinator in writing (or by email) of their intention.

If necessary, subjects may be terminated or withdrawn by the Principal Investigator without the consent of the participant if continued participation would be contraindicated, including because the participant (1) becomes pregnant (and therefore it would not be appropriate to follow a weight loss program); (2) develops a life threatening disease for which weight loss is contraindicated; (3) joins another weight control program (such as Weight Watchers, Jenny Craig, NutriSystems, etc.); or (4) the participant moves more than 120 miles from the clinical center with no plans to return during study assessment windows.

Sources of Materials: *Identify sources of research material obtained from individually identifiable human subjects in the form of specimens, records or data. Indicate whether the material or data will be obtained specifically for research purposes or whether use will be made of existing specimens, records or data.*

The anthropometric, behavioral, and self-report questionnaire data collected in this study will be obtained for research purposes only.

DRUG AND DEVICE INFORMATION

Investigators are encouraged to consult the UVM Medical Center Investigational Pharmacy Drug Service ([name]) prior to finalizing study drug/substance procedures.

Drug (s)

CHRBSS (Behavioral) #19-0131 Approved: 6/16/2019

Drug name – generic followed by brand name and common abbreviations. Availability – Source and pharmacology, vial or product sizes and supplier. If a placebo will be used, identify its contents and source. (attach investigational drug brochure)

Preparation: Reconstitution instructions; preparation of a sterile product, compounded dosage form; mixing guidelines, including fluid and volume required. Identify who will prepare.

Storage and stability – for both intact and mixed products.

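### Only serious adverse events have a stated recording step, so the pilot plans no count of minor harms, overall or by arm

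*Combined protocol and SAP*

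**What the plan says.** Two sections carry the same sentence, Data Safety and Monitoring (safety of the subjects) and Adverse Event and Unanticipated Problem Reporting: "Any serious adverse events will be recorded on a standard form", with onward reporting to the coordinator, the principal investigators and the IRB. In both, the only other surveillance named is that "Weekly meetings or conference calls will be held to evaluate the status of study participants". No form, event definition or table is attached to those meetings.

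On expected harms, Potential Risks states: "The most common risk associated with participation in the interventions is soreness or musculoskeletal injury, although this occurs infrequently". Protection Against Risk adds that "participants who experience other medical problems during the course of the study will be referred to their personal physician for care as appropriate", without saying that such problems are recorded.

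On what differs between arms, Study Design says it is only active lessons against observed demonstrations. In the active arm, under The Cooking Program, "Participants work in teams of two in the NFS foods lab to actively practice skills and cook a meal", and the handouts include knife skills and equipment. The same section lets participants in both arms taste the prepared food.

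On data capture, Procedures states that "weekly data collection will be administered through the study website".

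**The concern.** The recording rule and the risk statement do not fit together. The risk named as most common is one that will usually be non-serious, and the rule reaches serious events only. The one component that differs between the arms is practical work in a kitchen, done by people who at entry cook from scratch no more than three meals a week. The risk section discusses diet, exercise and confidentiality and does not mention kitchen or food hazards.

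What is at stake is the pilot's use as preparation for a larger study, which Number of Subjects gives as the purpose of these data. If the plan is followed as written, an absence of minor events in the report could not be told apart from an absence of recording. The weight and diet-quality comparisons are not touched.

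**Working it through.** The plan states no safety figure, so the main check is a reading of every place where a non-serious harm could be captured.

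1. **Recording rule.** Data Safety and Monitoring and the adverse event section both cover serious events only. The documents do not define serious.
2. **Surveillance.** There are weekly staff meetings or calls, review of self-monitoring diaries for nutritional adequacy, and referral of other medical problems to the personal physician. None has a stated recording step for harms.
3. **Measures.** The measures listed in Table 1 and described under Procedures are diet recall and its index, two cooking questionnaires, weekly cooking frequency, height, weight and BMI, demographics, photo elicitation and the class evaluation. None is described as asking about adverse events.
4. **Analysis.** Statistical Considerations covers Aims 1 and 2 by repeated-measures models, and Aim 3 by attendance, self-monitoring and qualitative usefulness. There is no safety summary, overall or by arm.
5. **Form prompt.** The template text in the adverse event section asks how events and unanticipated problems will be evaluated, and asks that the institutional policy be specified. The reply covers serious events only and does not name the policy.

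**Which harms differ by arm**

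| Harm | COOKING | DEMONSTRATION | Basis |
|---|---|---|---|
| Musculoskeletal | possible | possible | same weight-loss program in both arms |
| Food reaction | possible | possible | both arms may taste the food |
| In-class cut or burn | possible | observers only | inferred from the hands-on work |

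**Scale (illustrative)**

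- Sample size: 16 places x 2 arms x 2 waves = 64, which reproduces the stated total and gives 32 per arm.
- Exposure in the COOKING arm: 32 x 12 classes = 384 person-classes. This is a maximum, because it assumes full enrolment and full attendance.
- Expected minor injuries at an assumed 0.5-1% per person-class: 384 x 0.005 = 1.9 and 384 x 0.01 = 3.8.
- Chance of at least one affected participant in an arm of 32, 1 - (1 - p)^32, at assumed participant-level rates: 48% at 2%, 81% at 5%, 97% at 10%.
- If events were recorded and none seen in 32, the one-sided 95% upper bound would be 1 - 0.05^(1/32) = 8.9%.
- Power of a between-arm test with 32 per arm, again at assumed rates: 27% for 2% against 10%, and 44% for 5% against 20%.

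So an arm of this size would probably show ordinary minor events if their rate were 5-10% and they were recorded. It could not support a comparison, and counts would have to be descriptive.

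**The case against.** The best case against the point is proportionality. This is a low-risk behavioral pilot. The template text under Data Safety and Monitoring allows a minimal-risk study a very simple monitoring plan. Facilitators take part in monitoring, a chef runs every session, status is reviewed weekly, and the class evaluation in both arms could bring out bad experiences. Attached instruments and consent pages are not in the text available here and may hold more. No hypothesis test, estimate or sample size depends on the missing data.

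Most of this stands, and it limits the point to a modest one. It does not supply a recording step. Low risk justifies light monitoring, but the stated rule still restricts what is collected, and a meeting that notices an event leaves no count unless someone writes it down.

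A reader might be tempted by stronger readings that the documents do not support:

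- **That kitchen injuries would never be recorded, or that the report would be clean whatever happened.** A cut, burn or reaction that met a serious definition would go on the form and to the IRB. The plan also does not say that nothing else may be documented.
- **That food reactions or musculoskeletal problems are peculiar to hands-on cooking.** Both arms may taste the food and both receive the same activity advice.
- **That Aim 3 as written already calls for harms data.** It is defined by attendance, self-monitoring and perceived usefulness.
- **That two to four unrecorded injuries are to be expected.** The rate behind that figure is an assumption.

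**Conclusion.** The point holds in limited form. The only stated recording rule covers serious events, and no listed measure or analysis provides for any other harm. Minor harms, including most instances of the plan's own leading risk, would therefore have no planned count in either arm. Only in-class cut and burn exposure distinguishes the COOKING arm, and that hazard is inferred from the kitchen work.

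The primary outcome and the tests under Aims 1 and 2 are unaffected. The loss is descriptive information on minor harms for the larger study. Its size is unknown: about 2-4 events is what an assumed 0.5-1% of at most 384 person-classes gives, and lower attendance reduces it in proportion. The conclusion assumes that the attached instruments, which were not available, contain no adverse event item. The change is worth making but does not block the trial.

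**What to change.** 1. Add one adverse event item, yes/no with free text, to the weekly online form that both arms already complete. Identical wording and timing keep ascertainment the same in each arm.
2. Keep the same brief incident log at every cooking class and every demonstration, including an explicit entry when nothing occurred.
3. Add a sentence to Statistical Considerations: report counts of events and of affected participants by arm, descriptively, with no between-arm test.
4. Name kitchen and food hazards in Potential Risks.
5. Complete the adverse event section by naming the institutional reporting policy that its prompt asks for.

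The cost is a protocol amendment and some staff time, with no added visits. At full participation the item yields up to 64 x 24 = 1,536 weekly responses, of which only those marked yes need free-text review. The log covers 12 sessions x 2 arms x 2 waves = 48 sessions. Asking every week in a program with an exercise component will draw some trivial reports, and the plan should say who reviews them.
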